Study size	
Based on the patient count estimations, the expected total study size in the four target countries (Denmark, France, Spain, and Sweden) is about 850 children under two years with VTE, with approximately 280 of them using rivaroxaban oral suspension.
 
All children from the target population present in the data sources will be analysed.

Data analysis	
Descriptive analyses by data source
 
Categorical variables will be presented as counts (n) and proportions (%), with 95% confidence intervals (CI) where relevant. Continuous variables will be presented as means with standard deviation and as medians with interquartile range, where appropriate.
 
The following descriptive analyses will be presented:
 
 • Patients' characteristics according to exposure category (rivaroxaban or SOC), with stratification on the status of exposure, i.e., initiators versus switchers • Drug utilization patterns of initial therapy and maintenance therapy (dose, frequency, route of administration, treatment duration, treatment switch)

	
 • Crude incidence rate, cumulative incidence and Kaplan-Meier analysis of the safety and effectiveness outcomes, using an as-treated exposure definition. Sensitivity analyses will be applied for the exposure (considering only the first treatment agent episode) and for the safety and effectiveness outcomes (considering a more restrictive definition). 
Combined descriptive analyses of aggregated data across data sources
 
 • Characteristics of patients and drug use patterns • Safety and effectiveness outcomes (if sample size allows)
Milestones	
Start of study period: market entry date of rivaroxaban oral suspension in each country
 
Start of data collection: 12 months from the PRAC endorsement of the full study protocol
 
End of data collection: Q2 2029
 
Study progress report: Annually, from Q4 2023 to Q4 2027
 
Final report of study results: Estimated Q4 2029
 
The annual progress reports will allow to monitor the uptake of rivaroxaban oral suspension and follow-up the number of patients for the study population as well as opportunities to finalize the study earlier.

5. Amendments

None

6. Milestones

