9.1. Study design

This will be an observational, retrospective, descriptive, multi-national cohort study of children initiating anticoagulation therapy. The study will be conducted using secondary data derived from multiple data sources including electronic health records and administrative health insurance claims data in four European countries (France, Sweden, Denmark, Spain).

The study cohort will include all children aged under two years and initiating anticoagulant therapy following a VTE diagnosis. The inclusion period will be from the market launch date of rivaroxaban oral suspension in each country until end of 2026, with follow-up until end of 2027. Patients will be followed up from the anticoagulation therapy initiation (index date), until occurrence of bleeding (major bleeding, and CRNM bleeding as co-primary outcomes) or recurrent symptomatic VTE (as secondary outcome) – with time at risk specific to each outcome, discontinuation of all study drugs, death, exit or last available data from the data source, or end of study period, whichever occurs first. Two exposure categories will be defined, one for rivaroxaban and one for SOC, using an as-treated exposure definition. Patients will contribute time to both exposure categories if they switch from SOC to rivaroxaban or vice versa. As long as the anticoagulant treatment period is continuing, patients will be allowed to switch multiple times between SOC and rivaroxaban and contribute time accordingly to both exposure categories.

[figure not shown]
If patients have another initiation of anticoagulant therapy for a VTE diagnosis before the age of two years, and for which they fulfil all inclusion and exclusion criteria (including a 6-month washout period), they will be allowed to enter the study cohort again with a new index date.

22195; XAPAEDUS; v 2.1, 16 NOV 2022;

Page 17 of 59

based on template version 9

An overview of the study design is presented in [Figure 1](#).

DOAC = direct oral anticoagulant; SOC = standard of care; VKA = vitamin K antagonist; VTE = venous thromboembolism

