9.2.2.2. Study period

At this stage it is assumed that the study will last at least seven years to provide enough time to ensure the achievement of the sample size (see [Section 9.5](#)). The inclusion period will start on the market launch date of rivaroxaban granules for oral suspension 1 mg/mL in the respective countries. The countries were selected based on the potential data sources that were investigated during the feasibility phase (see [Section 9.4.1](#)). A description of market authorization status in the different potential countries along with launch date is provided in [Table 2](#).

The study period would end 31 DEC 2027, with the inclusion period ending 31 DEC 2026 to allow a minimum potential follow-up of 12 months.

Table 2: Market presence of rivaroxaban granules for oral suspension 1 mg/mL (as of August 2022)

Country	Marketing authorization status	Marketing authorization date	Reimbursement status	Reimbursement date	Market entry date	Distribution channel ^a	Availability of rivaroxaban oral suspension after market penetration ^b
Denmark	Granted	February 2021	Y	17/05/2021	October 21	Hospital and Retail	High
Finland	Granted	February 2021	Y	08/05/2021	September 2021	Hospital and Retail	High
Sweden	Granted	February 2021	Y	22/10/2021	September 2021	Hospital and Retail	High
France	Granted	February 2021	Y	18/04/2022	April 2022	Hospital and Retail	High
Germany	Granted	February 2021	Y	21/01/2021	May 21	Hospital and Retail	High
Italy	Granted	February 2021	N	Expected September 2022	Pending	Pending	Moderate
Netherlands	Granted	February 2021	Y	07/01/2021	July 2021	Hospital and Retail	High
Spain	Granted	February 2021	N	Pending	Pending	Hospital and Retail	Moderate
UK	Granted	February 2021	Y	21/01/2021	April 2021	Hospital and Retail	High
Canada	Granted	January 2021	N	Pending	May 2021	Pending	High

^a Retail pharmacy, hospital pharmacy, other institutional care

^b High (marketing authorization and reimbursement obtained, and has entered market), moderate (marketing authorization obtained, but reimbursement and/or market entry pending), poor (marketing authorization, reimbursement and market entry pending)

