9.4. Data sources

9.4.1. Feasibility assessment

The study will make secondary use of existing data from multiple countries. A feasibility assessment was conducted with the aim to evaluate large electronic healthcare databases to guide the selection of the most relevant data sources for addressing the research question and study objectives. A report on this feasibility assessment is provided as a stand-alone document (see [Annex 1](#)) which is available upon request.

The choice of final data sources was guided by the following criteria:

- Representativeness of the overall population covered by the data source and the target population of children under two years with VTE receiving anticoagulant therapy
- Countries in which the estimated cumulative average number of children under two years with VTE and exposed to rivaroxaban in the data source is at least 15 during the inclusion period 2021-2026 (see [Section 9.5.2](#))
- Availability of the information required to meet the study objectives, including the ability to identify and describe the target population of children under two years with VTE, and the availability and quality of exposure and outcomes data
- Procedure and timelines for data access
- Coverage of different regions in Europe

Based on the overall rating, the final list of recommended data sources include:

- Système National Des Données De Santé (SNDS) in France
- National health registers in Sweden
- National health registers in Denmark
- Sistema d'Informació per al Desenvolupament de l'Investigació en Atenció Primària (SIDIAP) in Spain

Depending on the actual accrual of patients over the study period, additional data sources might need to be considered in future.

General characteristics of the data sources are provided in [Table 3](#).

Table 3: Summary characteristics of data sources

Country	Data source name	Data source type	Population size (active)	Source population coverage (%)	Data lag time	Coding system for drugs	Drugs data	Coding system for diagnoses	Diagnoses and procedures data
Denmark	MBR, NPR, RMPS, SMR, Register of causes of death	National health registers	5.8 million	100%	2-13 months	ATC	Drugs dispensed at community pharmacies. Drugs given in hospitals (expected release in 2022)	ICD-10	Secondary outpatient care, inpatient care, emergency

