9.5.2. Estimation of patient counts

It is assumed that four countries will be targeted to collect the data from the respective country's data source. The actual study size will depend on the number of final selected data sources, product uptake over time and study duration. All paediatric patients from the target population present in the selected data sources will be analysed. An estimation of patient counts is provided in [Table 6](#). The method to estimate the patient count comprised two steps:

- First step consisted in estimating the cumulative number of children under two years with VTE in each data source over an inclusion period of 2021-2026. This estimation was based on the following parameters: i) the incidence rate of VTE in the general paediatric population, ranging from 0.14 to 0.49 per 10,000 patients (2); ii) the percentage of patients under two years among children with VTE, ranging from 20% to 25% (19); iii) the population size of children in each country; and iv) the data source coverage in each country. The cumulative number of children under two years with VTE were provided for each data source with three estimates: the lowest estimate was based on incidence rate of VTE of 0.14/10,000 and 20% of children under two years among children with VTE; the highest estimate was based on incidence rate of VTE of 0.49/10,000 and 25% of children under two years among children with VTE; finally, an average estimate was reported as the mean of the lowest and the highest estimates. For instance, the average estimate of the cumulative number of children under two years with VTE included over 2021-2026 ranges from 45 children in SIDIAP in Spain to 650 children in SNDS in France.
- Second step consisted in estimating the number of those paediatric patients exposed to rivaroxaban oral suspension. This estimation was based on assumptions of market share of the product over the period of 2021-2026: 10% in 2021, 32% in 2022, 38% in 2023, 42% in 2024, 50% in 2025 and 30% in 2026. Similarly, to the first step, a lowest, a highest and an average estimate were provided for each data source. As a result, the average estimate of the cumulative number of children under two years with VTE and exposed to rivaroxaban oral suspension ranges from 15 patients in SIDIAP in Spain to 219 patients in SNDS in France.

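### The expected study size counts six full years in every country although inclusion starts only at launch: about 680 children rather than 846, and about 260–270 on rivaroxaban rather than 285

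*Protocol*

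**What the plan says.** On the inclusion window, section 9.1 states: "The inclusion period will be from the market launch date of rivaroxaban oral suspension in each country until end of 2026". Section 9.2.2.2 repeats it: "The inclusion period will start on the market launch date of rivaroxaban granules for oral suspension 1 mg/mL in the respective countries". It sets the close "with the inclusion period ending 31 DEC 2026 to allow a minimum potential follow-up of 12 months". The rule covers the whole cohort, so children on standard of care also enter only from launch.

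Table 2 (as of August 2022) gives market entry as September 2021 for Sweden, October 2021 for Denmark and April 2022 for France. Spain is pending for both reimbursement and market entry. It is rated moderate, which the footnote defines as "marketing authorization obtained, but reimbursement and/or market entry pending".

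On study size, section 9.5.2 describes "estimating the cumulative number of children under two years with VTE in each data source over an inclusion period of 2021-2026". It then applies one series of calendar-year market shares to every source: 10%, 32%, 38%, 42%, 50% and 30% for 2021 to 2026. The abstract and section 9.5.2 conclude that the expected size "is about 850 children under two years with VTE, with approximately 280 of them using rivaroxaban oral suspension". Section 9.5.3 repeats the 280.

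On source selection, one criterion in section 9.4.1 is that the average estimated number of children "exposed to rivaroxaban in the data source is at least 15 during the inclusion period 2021-2026". SIDIAP is listed at exactly 15.

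**The concern.** The size estimate and the design use different inclusion windows. France, which supplies 650 of the 846 children, is credited with 15 months before its launch, and Spain with at least 20. Both are also given rivaroxaban users in 2021, when Table 2 shows no product on either market. The protocol is dated November 2022, after the Table 2 dates were known.

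Three things rest on these counts: the headline size, the choice of SIDIAP as a source, and the margin by which bleeding on rivaroxaban is expected to be reportable in SNDS. SNDS is the only source where the protocol expects that analysis to be feasible.

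**Working it through.** **Reproducing the printed figures.** The average annual number in Table 6 is 141, and 141 × 6 = 846. The mean of the six shares is (10 + 32 + 38 + 42 + 50 + 30)/6 = 33.67%, and 846 × 0.3367 = 284.8, printed as 285. By source the same product gives Denmark 17.5 (printed 18), France 218.8 (219), SIDIAP 15.15 (15) and Sweden 33.0 (33). The table therefore uses six full years everywhere.

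**Inputs for the correction.** Annual average = printed cumulative number / 6. The window runs from the first day of the market-entry month to 31 December 2026. Spain is assumed to start on 1 September 2022, the earliest month consistent with Table 2.

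**All children** = annual average × years in window.

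| Source | Annual | Years | Result | Printed |
|---|---|---|---|---|
| France | 108.33 | 4.75 | 514.6 | 650 |
| Sweden | 16.33 | 5.33 | 87.1 | 98 |
| Denmark | 8.67 | 5.25 | 45.5 | 52 |
| SIDIAP | 7.50 | 4.33 | 32.5 | 45 |
| Total | | | 679.7 | 846 |

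1 − 679.7/846 = 19.7% lower. Spain from January 2023 gives 677, and from January 2024 gives 670. The same scaling of the lowest and highest estimates gives 191.6 + 32.9 + 16.6 + 12.3 = about 253 and 837.6 + 142.2 + 74.4 + 52.7 = about 1,107, against the printed 315 and 1,376.

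**Rivaroxaban users** = annual average × sum of the calendar-year shares inside the window. The shares for 2022–2026 sum to 1.92, and for 2023–2026 to 1.60. The protocol does not say whether a launch-year share applies only to the months after launch or is already an average over the whole year, so both readings are shown.

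| Source | Launch-year share pro-rated | Not pro-rated | Printed |
|---|---|---|---|
| France | 108.33 × (0.75 × 0.32 + 1.60) = 199.3 | 108.33 × 1.92 = 208.0 | 219 |
| Sweden | 16.33 × (0.333 × 0.10 + 1.92) = 31.9 | 16.33 × 2.02 = 33.0 | 33 |
| Denmark | 8.67 × (0.25 × 0.10 + 1.92) = 16.9 | 8.67 × 2.02 = 17.5 | 18 |
| SIDIAP | 7.5 × (0.333 × 0.32 + 1.60) = 12.8 | 7.5 × 1.92 = 14.4 | 15 |
| Total | 260.9 | 272.9 | 285 |

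The totals are 8.5% and 4.2% lower. If Spain starts in January 2023, SIDIAP is 7.5 × 1.60 = 12.0 on either reading, and the totals are about 260 and 270.5 (8.7% and 5.1% lower). If Spain starts in January 2024, SIDIAP is 7.5 × 1.22 = 9.2.

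**SIDIAP against 15.** Removing 2021 alone already gives 14.4. No start consistent with Table 2 reaches 15.

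**Rivaroxaban bleeds in SNDS** at 5.6%: printed basis 219 × 0.056 = 12.3; corrected 199.3 × 0.056 = 11.2 or 208 × 0.056 = 11.6. Section 9.7.8 suppresses French counts below ten.

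**A minor slip in the same table.** The all-children recurrent-VTE rows match the unweighted mean (1.2% + 3.0%)/2 = 2.1%: 846 × 0.021 = 17.8 (printed 18) and, in SNDS, 650 × 0.021 = 13.7 (printed 14). Weighting by the table's own split gives 285 × 0.012 + 561 × 0.030 = 20.2 and 219 × 0.012 + 431 × 0.030 = 15.6, so 20 and 16. For bleeding the two methods give 48.6 and 49.1 overall, both printed as 49.

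**The case against.** The study is descriptive, has no power calculation and analyses every eligible child. Section 9.5.2 says that the actual size depends on uptake and duration, section 9.5.3 promises annual monitoring, and section 9.4.1 allows further sources. The printed ranges (315–1,376 children, 106–463 on rivaroxaban) contain the corrected values. All of this stands and limits the harm: no test or analysis is invalidated. None of it reconciles the estimate with the inclusion rule, because monitoring future counts does not correct a baseline that includes months the design excludes.

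A reader might infer more than the documents support:

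- **That the 20% loss also applies to the 280 rivaroxaban users.** It does not on the protocol's calendar-year shares, since the lost months carry 10% and 32%. A loss of about 20% (to about 228) appears only if the uptake curve restarts at each launch, which the protocol does not say. That reading would also put France at 108.33 × 1.595 = 172.8 users and 9.7 expected bleeds.
- **That bleeding in SNDS becomes infeasible.** The corrected expectation stays above ten, and the printed range of 5 to 20 already admitted a shortfall.
- **That SIDIAP must be dropped.** The figure of 15 is one of several guiding criteria feeding an overall rating. Regional coverage and linkage to hospital drug data may justify keeping SIDIAP. The miss is one to three children if Spain starts by January 2023, on an estimate with a printed range of 6 to 25.
- **That the target of 29 per source in section 9.5.3 is newly missed.** Sweden still meets it (32–33). Denmark and SIDIAP were already below it on the printed counts.

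**Conclusion.** The point holds: Table 6 describes a window that the design does not have. The total is about 680 rather than 846 (20% lower), with France responsible for about 135 of the roughly 166 children lost. Rivaroxaban users are about 260–270 rather than 285. SIDIAP falls to about 12–14 against a criterion of at least 15, or lower if Spain launches after January 2023. The expected number of rivaroxaban bleeds in SNDS keeps a thinner margin over ten, and the feasibility conclusion does not change.

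The result assumes the protocol's constant annual VTE counts, its calendar-year shares, entry from the first day of the market-entry month, and a Spanish start no earlier than September 2022. The Spanish date affects the total by only about ten children between September 2022 and January 2024. The recurrent-VTE weighting is a real but minor error, in a secondary outcome.

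**What to change.** Recompute Table 6 with country-specific windows from launch to 31 December 2026. State the assumed Spanish launch date, and say whether launch-year shares are pro-rated. Carry the results into the abstract and sections 9.5.2–9.5.3: about 680 children and about 260–270 on rivaroxaban, with new lowest and highest estimates.

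Re-apply the 15-patient criterion in section 9.4.1 to SIDIAP, or state that SIDIAP is kept on the other criteria. In the same revision, weight the all-children recurrent-VTE rows by the table's rivaroxaban/comparator split. On the current counts this gives 20 overall and 16 in SNDS, and both should then be recalculated on the corrected windows.

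The cost is one recalculated table and a few sentences. Design, data access and analyses are unchanged, and the stated size becomes less favourable.

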9.5.3. Monitoring of actual patient counts

The number of patients for the study population that accrue in the data sources will be monitored over time in order to decide when to launch the analyses.

The strategy for this monitoring will depend on the two following data source conditions:

- In data sources where patient count and/or data extraction is feasible before the study conduct itself, the actual number of children with VTE receiving rivaroxaban oral suspension will be monitored annually, per calendar year and cumulatively.
- In data sources where this is not feasible, patient counts as estimated in [Section 9.5.2](#) will be updated based on the actual sales data of rivaroxaban oral suspension.

These actual patient count estimates will be reported annually for each data source as part of progress reports.

Based on the patient count estimates (see [Section 9.5.2](#)) and the required number of patients for a precision level of 10% for the 95% CI of an outcome with a 5% incidence (see [Section 9.5.1](#)), it is anticipated that the study should last at least seven years (inclusion period from 2021 to 2026 with follow-up until end of 2027) to include at least 29 children under two years with VTE and receiving rivaroxaban oral suspension per data source. As explained above, the total of those patients in the four countries is expected to be approximately 280.

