9.5. Study size

9.5.1. Estimation of sample size

This study is descriptive in nature with no intent for hypothesis generating or testing, and thus does not require power calculation. This study will be conducted on several data sources from different countries, with different degree of coverage, and all patients fulfilling inclusion and exclusion criteria will be analysed.

The sample size estimation according to different levels of precision and proportion of interest is proposed below. The size of the sample population will determine the precision of the estimations, measured as the range of their 95% CI. The assumptions for the precision estimation are based on the results of bleeding and recurrent VTE events from the pivotal Phase III EINSTEIN Junior study (6). The incidence of CRNM bleeding among children under two years old was 5.6% with rivaroxaban and 5.9% with comparator, while the incidence of recurrent VTE among children was 1.2% and 3.0% for rivaroxaban and comparator, respectively.

Table 5 shows the required number of patients by acceptable precision (95% CI) and proportions of interest using the exact approximation formula for CI for proportions.

For example, for an outcome with an incidence of 5%, at least 94 patients are required for a precision of 5% for the 95% CI, and 29 patients are required for a precision of 10%.

Table 5: Required number of patients by acceptable precision (95% CI) and proportions of interest using the exact approximation formula for CI for proportions

Proportion of interest	Margin of error for 95% CI (absolute precision)		
	5%	7.2%	10%
0%	35	24	17
1%	43	28	19
3%	67	37	23
5%	94	50	29
8%	133	68	38
10%	157	80	43

CI = Confidence interval

Exact approximation formula according to the Clopper-Pearson method.

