Then, for each data source and population (i.e., overall study population and subgroup of patients with rivaroxaban oral suspension), the lowest, highest, and average number of expected outcomes were estimated by using the incidence rates of the pivotal Phase III EINSTEIN Junior study as reference for the CRNM bleeding (5.6% with rivaroxaban, 5.9% with comparator) and the VTE events (1.2% with rivaroxaban, 3.0% with comparator).

Over 2021-2026, an average of 650 children under two years with VTE would be identified in the SNDS (range from 242 to 1058), with an average of 219 of them (range 81-356) using rivaroxaban oral suspension, and an average of 12 of them (range 5-20) having a bleeding with hospitalization. In the Swedish national registers, this would lead to an average total of 98 children under two years with VTE (range 37-160), with 33 of them receiving rivaroxaban oral suspension (range 12-54), and 2 of them with a bleeding with hospitalization (range 1-3). In the Danish national registers, an average total of 52 children under two years with VTE (range 19-85) is expected, with 18 of them receiving rivaroxaban oral suspension (range 7-29), and 1 of them with a bleeding with hospitalization (range 0-2). In SIDIAP, we could expect an average total of 45 children under two

years with VTE (range 17-73), with 15 of them receiving rivaroxaban oral suspension (range 6-25), and 1 of them with a bleeding with hospitalization (range 0-1).

Based on these patient count estimations, the expected total study size in the four target countries (Denmark, France, Spain, and Sweden) is about 850 children under two years with VTE, with approximately 280 of them using rivaroxaban oral suspension.

Of note, small cell counts must be suppressed in results from all data sources to mitigate the risk of re-identification. Due to the small sample size and low frequency of the outcomes, it is expected that the outcomes analysis with respect to bleedings and recurrent VTE should only be feasible in the SNDS (as shown in [Table 6](#)).

Table 6: Estimation of patient counts

Country - Data source(s)	Denmark national registers	France SNDS	Spain SIDIAP	Sweden national registers	Overall
Children <2y with VTE^a					
Annual number					
Lowest estimate	3	40	3	6	52
Highest estimate	14	176	12	27	229
Average estimate	9	108	7	16	141
Cumulative number of patients over 2021-2026					
Lowest estimate	19	242	17	37	315
Highest estimate	85	1058	73	160	1376

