9.7.8. Combined analysis across data sources

In addition to separate analysis in each data source, descriptive analyses combining cumulative aggregated data of each individual data source will be conducted when possible.

According to GDPR, values must be suppressed whenever a patient count is less than a defined threshold: less than five cases/observations in the Nordic countries, less than six in Spain, and less than ten in France.

Therefore, combined analyses should be possible for characteristics of patients and drug use patterns. However, due to the small sample size and rarity of the outcomes bleedings and recurrent VTE, it is expected that these analyses should only be feasible in the SNDS, in which case combined analyses of outcomes across data sources would not be possible.

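### Section 9.5.3 justifies the seven-year duration by at least 29 rivaroxaban children per data source, but the Table 6 estimates it cites average 18 in Denmark and 15 in SIDIAP

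*Protocol*

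**What the plan says.** Section 9.5.1 sets precision targets for a descriptive study. It says precision is "measured as the range of their 95% CI", while the header of Table 5 labels its columns as margin of error (absolute precision). For an outcome with 5% incidence, Table 5 gives 29 patients at 10% and 94 at 5%.

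Section 9.5.3 carries the 29 forward. Citing the patient counts of Section 9.5.2 and "the required number of patients for a precision level of 10% for the 95% CI of an outcome with a 5% incidence", it anticipates a duration of at least seven years "to include at least 29 children under two years with VTE and receiving rivaroxaban oral suspension per data source".

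Section 9.5.2 and Table 6 cover the same 2021-2026 inclusion period. For Denmark they give a total "with 18 of them receiving rivaroxaban oral suspension (range 7-29"), and for SIDIAP a total "with 15 of them receiving rivaroxaban oral suspension (range 6-25"). Sweden is put at 33 (12-54) and SNDS at 219 (81-356). Section 9.4.1 selects countries in which the estimated average number "exposed to rivaroxaban in the data source is at least 15 during the inclusion period 2021-2026".

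Section 9.7.8 gives the suppression limits: "less than five cases/observations in the Nordic countries, less than six in Spain, and less than ten in France". Sections 6, 9.5.2, 9.7.8 and 9.9 and Table 4 say that bleeding is expected to be analysable only in SNDS or the largest source(s).

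**The concern.** Section 9.5.3 names Section 9.5.2 as its basis, so the two should agree. They do not: two of the four sources are expected to fall well short of the number used to justify the study's length. A reader of the study-size section would conclude that each source will estimate a 5% incidence to within 10 points, when half of them are not expected to.

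The statement is also the only numeric per-source target in the section on monitoring patient counts. Those counts inform when the analyses are launched, and the annual progress reports look for chances to finish earlier. A benchmark that two sources are not expected to reach, and that SNDS passes even on its lowest estimate, is of little use for that judgement.

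**Working it through.** **Inputs.** Target 29, 5% incidence, 10% precision, Clopper-Pearson (Section 9.5.1, Table 5; Section 9.5.3). VTE and rivaroxaban counts and yearly market shares (Section 9.5.2, Table 6). Reference bleeding incidence with rivaroxaban 5.6% (Section 9.5.1). Suppression limits (Section 9.7.8).

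**1. Reproduce the 29.** Take the Clopper-Pearson 95% interval with x = n × p, non-integer x allowed:
- lower limit = Beta quantile at 0.025 with parameters (x, n − x + 1)
- upper limit = Beta quantile at 0.975 with parameters (x + 1, n − x)
- half-width = (upper − lower)/2

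For n = 29 and p = 0.05, x = 1.45. The interval is 0.3% to 20.1% and the half-width 9.87 points. For n = 28 the half-width is 10.08, so 29 is the smallest n that meets 10. The same rule gives every Table 5 cell to within one patient. Reading the 10% as the full width would need 94 patients, so Table 5 holds half-widths.

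**2. Reproduce the Table 6 rivaroxaban counts.** Mean market share = (10 + 32 + 38 + 42 + 50 + 30)/6 = 33.67%. Multiplying the average VTE counts:
- Denmark 52 × 0.3367 = 17.5 (Table 6: 18)
- SIDIAP 45 × 0.3367 = 15.2 (15)
- Sweden 98 × 0.3367 = 33.0 (33)
- SNDS 650 × 0.3367 = 218.8 (219)

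The counts are internally sound. The conflict lies between them and the 29.

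**3. Set 29 against Table 6, with the resulting half-width at 5%.**

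| Source | Lowest n: half-width | Average n: half-width (95% CI) | Highest n: half-width | Reaches 29 on |
|---|---|---|---|---|
| Denmark | 7: 23.8 | 18: 13.2 (0.1-26.5%) | 29: 9.9 | highest only |
| SIDIAP | 6: 26.0 | 15: 14.8 (0.04-29.6%) | 25: 10.8 | none |
| Sweden | 12: 17.0 | 33: 9.1 (0.4-18.7%) | 54: 6.8 | average, highest |
| SNDS | 81: 5.4 | 219: 3.1 (2.5-8.8%) | 356: 2.4 | all |

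Sources missing 29: three of four on the lowest estimate, two on the average, one on the highest.

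**4. Time to reach 29 at the average six-year rate.** Denmark 29/(18/6) = 9.7 years. SIDIAP 29/(15/6) = 11.6 years. The planned inclusion period is six.

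**5. What 29 means for the bleeding objective.** Expected bleeds = 29 × 0.05 = 1.45. The binomial chance of at least 5 is 1.4%. In SNDS, where counts below 10 are suppressed, the chance of at least 10 bleeds (major and CRNM combined) is:

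| Rivaroxaban children in SNDS | at 5.6% | at 5% |
|---|---|---|
| 81 | 1.5% | 0.7% |
| 219 | 79% | 66% |
| 222 | 80% | 68% |
| 249 | 89% | 80% |

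An 80% chance therefore needs 222 children at 5.6% or 249 at 5%.

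**The case against.** The defence is strong on several points, and most of them stand.

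- **Suppression is disclosed.** A reader might infer that the 29 conceals an unreportable bleeding estimate. The documents do not support that: Table 4 marks bleeding as below threshold in Denmark, SIDIAP and Sweden, and several sections say outcomes are expected to be feasible only in SNDS. SNDS itself expects 12 bleeds among 219 rivaroxaban children, above its limit of 10.
- **29 is not a launch rule.** A reader might infer that a source would be declared ready at 29. Section 9.5.3 says counts inform the launch but attaches no number to that decision. The 29 appears only as an anticipated consequence of the study length. The end dates are fixed in Section 9.2.2.2, all eligible children are analysed, and Section 9.4.1 allows for additional sources.
- **Denmark can reach the target.** Its highest estimate of 29 satisfies a minimum of 29, so only SIDIAP misses in every scenario.
- **Table 5 is not miscalculated.** Its header says margin of error and its numbers are half-widths. Only the sentence in Section 9.5.1 is loose.
- **The threshold of 15 is not a contradiction in itself.** It is one of five source-selection criteria and serves a different purpose from precision.

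None of this reconciles 18 and 15 with a minimum of 29. The expectation that only SNDS can report bleeding also weakens the case for a per-source count as the yardstick.

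**Conclusion.** The inconsistency is real and should be fixed. The size and precision stated for every data source are not supported by the estimates cited for them. At the average counts, the half-width is 13.2 points in Denmark and 14.8 in SIDIAP against the stated 10. Sweden (9.1) and SNDS (3.1) meet the target.

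The count of two failing sources holds for the average estimate, which also underlies the protocol's total of about 280. The half-widths assume 5% incidence and the protocol's own Clopper-Pearson convention with x = np. The SNDS figures further assume that the trial's 5.6%, or 5%, applies to hospitalised bleeding in routine care. Section 7.2 shows that the 5.6% rests on two events among 36 children (21 + 15).

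The effect is confined to the justification of study length and to the benchmark for judging accrual. No analysis, population or planned outcome changes, so the point does not invalidate the study.

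**What to change.** 1. **Section 9.5.3:** remove the claim of at least 29 per data source. State instead the expected half-width and CI limits for each source at the lowest, average and highest Table 6 counts, as in step 3 above. Rest the duration on those figures.
2. **Section 9.5.1:** describe precision as half the width of the 95% CI, to match the Table 5 header. Show the limits alongside, for example 0.3% to 20.1% for 29 patients at 5%.
3. **Bleeding objective:** judge accrual against a rivaroxaban patient count in SNDS, about 222 children at 5.6% or 249 at 5%, for an 80% chance of at least 10 bleeds. Say that this refers to major and CRNM bleeding combined. The two are mutually exclusive co-primary outcomes, so the count does not ensure that each is reportable. Do not use a number of observed bleeds as the trigger: timing would then depend on the outcome being estimated, which can bias the incidence.

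The cost is protocol wording. The stated precision becomes less favourable in Denmark and SIDIAP. No extra patients are needed: the SNDS count is a benchmark for timing and early completion, and any shortfall against it at the end of inclusion would simply be reported.
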